## **6.4. Covariates and Subgroups**

The protocol does not define any formal subgroup analyses, and the study is not adequately powered to perform subgroup analyses.

## **6.5. Handling of Missing Data, Outliers, and BQL Data**

### **6.5.1. Missing Data**

All attempts will be made to collect all data per protocol. No imputation will be performed for missing values.

### **6.5.2. Outliers**

Outliers will not be excluded from the primary analyses. Outliers identified during the PK analysis will be discussed in the analysis report. Outliers will be defined as any values of plasma concentration for a given

---

treatment group that fall outside the interquartile fences of their respective distribution. Given an interquartile range (IQR) of Q3-Q1, where Q3 is the 75th percentile and Q1 is the 25th percentile, outliers will be those that are greater than Q3 + (1.5 x IQR) or those less than Q1 – (1.5 x IQR).

#### **6.5.3. BQL Data**

PK sample concentrations below the quantitative limit (BQL) will be imputed as zero if they did not come after a PK sample concentration that is above the lower limit of quantitation (LLOQ). The first PK sample that's BQL will be imputed as  $\frac{1}{2}$  LLOQ if it came after a PK sample concentration above LLOQ and all PK samples after are also BQL. Otherwise, PK sample concentrations that are BQL will be imputed as missing.

### **6.6. Interim Analyses and Data Monitoring**

Refer to [Section 6.2](#).

### **6.7. Multicenter Studies**

This is a single-site study.

### **6.8. Multiple Comparisons/Multiplicity**

The objectives of the study are to obtain safety data and plasma PK data for 3 escalating doses of SLV213 administered PO daily Q12h for seven days. There are no formal hypotheses being tested in this Phase 1 trial.

This study was terminated after Cohort 1 (400 mg) and will not proceed with sequential cohorts (600 mg and 800 mg).

## 7. STUDY SUBJECTS

### 7.1. Disposition of Participants

The composition of analysis populations, including reasons for participant exclusion, by treatment group, is presented in [Table 11](#).

The disposition of participants in the study will be tabulated by treatment group ([Table 10](#)). The table shows the total number of participants enrolled, included in Safety Population (receiving at least 1 dose), received all planned doses, included in the mITT population, included in PK population (having at least one quantifiable post dose plasma concentration), completed all PK blood draws, and completed follow-up.

A flowchart showing the disposition of study participant will be included ([Figure 2](#)). This figure will present the number of participants screened, enrolled, dosed, completed the study and/or lost to follow-up, and analyzed by treatment group.

A listing of participants who discontinued dosing or terminated from study follow-up and the reason will be included in [Listing 2](#). A listing of participants who were excluded from certain analysis populations and the reasons are included in [Listing 5](#).

### 7.2. Protocol Deviations

A summary of participant-specific protocol deviations will be presented by the reason for the deviation, the deviation category, and treatment group for all participants in the Safety Population ([Table 5](#)). All participant-specific protocol deviations and non-participant specific protocol deviations will be included in [Appendix 3](#) as data listings ([Listing 3](#) and [Listing 4](#) respectively).

## **8. EFFICACY EVALUATION**

There are no efficacy endpoints for this trial.

## 9. SAFETY EVALUATION

All safety analyses will be performed using the Safety Population and will be presented by Treatment Group. TEAEs will be presented in listings and summarized. Individual results of laboratory tests, VS, and ECGs will be listed and baseline, post dose, and changes from baseline to post dose laboratory, VS, and ECG data will be summarized.

In general, TEAEs, including abnormal laboratory values, will be graded according to the FDA Guidance: Toxicity Grading Scale for Healthy Adult and Adolescent Volunteers Enrolled in Preventive Vaccine Clinical Trials (<https://www.fda.gov/media/73679/download>). Grading scales are provided for AEs (**Table 6**), supine vital signs (**Table 7**), clinical laboratory results (**Table 8**), and ECG results (**Table 9**). Abnormal PE findings will be presented in data listings (**Listing 18**).

Clinical laboratory tests and VS at Screening Visit and Check-in (Day -1) should be within site normal reference range with exceptions as allowed per **Section 4.3.1**, inclusion criterion #4 and outlined in the Manual of Procedures (MOP). Grade 1 measurements acceptable at baseline will only be considered a TEAE post-baseline if condition worsened.

All TEAEs will be summarized using frequency counts and percentages. The following summaries will be presented for TEAEs and SAEs:

- Overall (i.e., regardless of severity or relationship to treatment).
- By severity grade (mild, moderate, severe, or life-threatening).
- By relationship to study drug.
- By MedDRA level hierarchy (system organ class [SOC], higher level group term [HLGT], and preferred term [PT]).

Unless otherwise specified, at each level of participant summarization in reporting the incidence of TEAEs, a participant will be counted once if the participant reported one or more TEAEs. If more than one occurrence of a TEAE is reported, the TEAE of the worst severity or the worst-case relationship assessment will be summarized.

### 9.1. Demographic and Other Baseline Characteristics

Summaries of sex, gender assigned at birth, ethnicity, and race and of age, height, weight, and BMI will be presented by treatment group (**Table 12** and **Table 13** respectively). Ethnicity is categorized as Hispanic or Latino, or Not Hispanic or Latino. In accordance with NIH reporting policy, participants may self-designate as belonging to more than one race or may refuse to identify a race, the latter reflected in the CRF as “No” to each racial option.

Individual participant listings (**Appendix 3**) will be presented for all demographics, including weight, height, and BMI (**Listing 6**), pre-existing medical conditions (**Listing 7**), and concomitant medications (**Listing 21**).

#### 9.1.1. Prior and Concurrent Medical Conditions

All current illnesses and pre-existing medical conditions will be Medical Dictionary for Regulatory Activities (MedDRA) coded using MedDRA dictionary version 24.1 or higher.

Individual participant listings will be presented for all medical conditions (**Listing 7**).

### 9.1.2. Prior and Concomitant Medications

All medications will be coded to the Anatomical Therapeutic Classification (ATC) using the current version of the World Health Organization (WHO) Drug Dictionary.

Individual participant listings will be presented for all concomitant medications ([Listing 21](#)).

### 9.2. Measurements of Treatment Compliance

Information on whether a participant missed a dose and reason, if provided, for missing a dose are included in [Listing 8](#).

### 9.3. Adverse Events

All AEs collected will be considered unsolicited. Unsolicited AEs collected after receiving the first dose will be considered TEAEs.

An overall summary of TEAEs by treatment group will be presented in [Table 22](#) including number and percentage of participants who experienced at least one TEAE and at least one SAE. The number and percentage of participants and the number of events will be presented for SAEs and AEs in [Table 23](#).

The following summaries of AEs will be presented by treatment group, SOC, HLGT, and PT:

- The number and percentage of participants, its corresponding 95% Confidence Interval (CI), and the number of events will be presented in [Table 24](#). The 95% CI will be calculated using exact Clopper-Pearson methodology.
- The number and percentage of participants will be presented by the maximum severity of each relationship to the study treatment (related or not related) in [Table 25](#).
- The frequency and incidence of related TEAEs are presented graphically in [Figure 9](#) and [Figure 10](#), respectively.

Individual participant listings will be presented for all TEAEs ([Listing 12](#)).

### 9.4. Deaths, Serious Adverse Events and other Significant Adverse Events

A complete listing of SAEs will be presented in [Table 26](#). Other non-serious, unsolicited, moderate or greater severity TEAEs are listed in [Table 27](#). A listing of adverse events of special interest (AESIs), medically attended adverse events (MAAEs), and unanticipated problems (UPs) will be presented in [Table 28](#).

### 9.5. Pregnancies

Individual data listings of pregnancy reports will be provided if a pregnancy occurs post dosing:

- Maternal information will be presented in [Listing 22](#).
- Gravida and para information will be presented in [Listing 23](#).
- Live birth outcomes will be presented in [Listing 24](#), and still birth outcomes will be presented in [Listing 25](#).
- Spontaneous, elective, or therapeutic abortion outcomes will be presented in [Listing 26](#).

## 9.6. Clinical Laboratory Evaluations

Venipuncture schedule and blood volumes are shown in schedule of assessments ([Table 3](#)). Unscheduled clinical laboratory evaluations will be included in listings of all clinical laboratory results but will be excluded from tabular and graphical summaries by time point, except when calculating the maximum severity post baseline. All clinical laboratory results will be listed for each participant from time of screening to last study visit. Any abnormal laboratory result at Screening or Check-in (Day -1) (baseline) with values in the Grade 1 range but deemed acceptable for enrollment per [Section 4.3.1](#), inclusion criterion #4, will be presented in listings but will only be reported as a TEAE if severity worsens. Clinical laboratory parameters that have grading criteria for both decreases (result lower than normal range) and increases (result higher than normal range) will be summarized separately by direction.

Laboratory results will be presented for chemistry, hematology, coagulation, and urinalysis separately. All safety laboratory results, severity, and change from baseline will be listed for each participant by treatment group, parameter, and time point in [Listing 13](#), [Listing 14](#), [Listing 15](#), and [Listing 16](#). Abnormal laboratory results (laboratory results outside the site normal range) will be presented in [Table 29](#), [Table 30](#), [Table 31](#), and [Table 32](#). Laboratory results outside of normal range but not within toxicity grading ranges will be listed as “ONR” (out of normal range) for severity.

The sort order for CHEM parameters will be as follows: Sodium, Potassium, Total Carbon Dioxide, Calcium, Chloride, Creatinine, eGFR, Blood Urea Nitrogen, Fasting Glucose, Total Protein, Albumin, Total Bilirubin, Direct Bilirubin, Alanine Aminotransferase, Aspartate Aminotransferase, Alkaline Phosphatase, Amylase, Lipase, Magnesium, and Inorganic Phosphorus.

The sort order for HEM parameters will be as follows: Hemoglobin, Platelets, Red Blood Cells, White Blood Cells, Neutrophils, Lymphocytes, Monocytes, Basophils, and Eosinophils.

The sort order for COAG parameters will be as follows: PT INR, Prothrombin Time, and aPTT.

The sort order for UA parameters will be as follows: pH, Specific Gravity, Bilirubin, Nitrite, Urine Protein, Urine Glucose, Occult Blood, White Blood Cell Count, Red Blood Cell Count, and Bacteria.

Laboratory results will be summarized for baseline, Day 2, Day 4, Day 6, and Day 8 in tables and figures:

- Number and percentage of participants with none, mild, moderate, severe, or life-threatening laboratory results both low (decrease) and high (increase) by parameter, time point, and treatment group for CHEM ([Table 33](#)), HEM ([Table 34](#)), COAG ([Table 35](#)), and UA ([Table 36](#)).

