All abnormal clinical findings or abnormal clinical laboratory test values post treatment will be considered AEs and followed up as AEs. If a physiologic parameter, e.g., VS or clinical laboratory value, is outside of the protocol-specified range, then the measurement may be repeated if, in the judgment of the participating site PI or appropriate licensed sub-investigator or clinician, the

abnormality is the result of an acute, short-term, rapidly reversible condition (e.g., stress, anxiety or “white coat syndrome”) or other source of error (e.g., a technical problem with the measurement caused by malfunctioning, or an inappropriate measuring device (i.e., inappropriate-sized BP cuff), or error in collecting or processing the clinical laboratory sample. If the repeat measure is within normal range, the most accurate value will be used. Any abnormal parameters will be recorded in the medical record.

Once dosed with study product, lab results that are above the upper limit of normal or below the lower limit of normal for the baseline reference ranges but are less than Grade 1 in the toxicity table, will not be graded and reported as outside the normal range. Lab results that were acceptable for enrollment within the Grade 1 toxicity range of the FDA toxicity tables will be graded as AEs if the on-study values are higher or lower than the baseline value and fall within the range of AEs with “increased” or “decreased” values.

Procedure followed for Abnormal Supine Vital Signs (Post Dosing On Days 1 through 9, or ET):

- Any time after the start of the oral dose administration, any abnormalities in supine VS that occur either due to technical or procedural error or the result of an acute, short-term condition as assessed by the PI (e.g., stress, anxiety, white coat syndrome) may be repeated twice more at rest, while the participant is in the supine position and at least 5 min of each other.
- If the second VS is abnormal, then the highest severity grade between the first and second measurements will be used for assessment of TEAE per [Appendix A](#).
- If the second VS is normal, then a third repeat is to be taken at least 5 min of the previous measurement.
- If the third value is abnormal, the highest grade of severity between the first and third measurements will be used for assessment of TEAE per [Appendix A](#).

8.3.4 Blood sampling for Plasma SLV213 Assay during the In-patient Period and Serum for Future Research

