#### 4.5.1. Safety Variables

Venipuncture schedule and blood volumes are shown in schedule of assessments ([Table 3](#)). The following safety endpoints will be assessed:

- Chemistry (CHEM), Hematology (HEM), Coagulation (COAG), and Urinalysis (UA) clinical laboratory result safety parameters will be collected at Screening, Day -1, and prior to the morning dose on Days 2, 4, and 6, and on Day 8 or at early termination.
  - CHEM parameters: Electrolytes (sodium, potassium, total carbon dioxide [CO2]), calcium, chloride, creatinine, blood urea nitrogen (BUN), fasting glucose, total protein, albumin, total bilirubin, alanine aminotransferase (ALT), aspartate aminotransferase (AST), alkaline phosphatase (ALP), amylase, lipase, magnesium, and inorganic phosphorus.
    - Note 1: Estimate glomerular flow rate (eGFR) and direct bilirubin will be collected but not graded.
  - HEM parameters: Hemoglobin, platelets, white blood cells (WBC), neutrophils, lymphocytes, monocytes, basophils, and eosinophils.
    - Note 1: Red blood cells (RBC) will be collected but not graded.
  - COAG parameters: Prothrombin time and activated partial thromboplastin time (aPTT).

- Note 1: Prothrombin time international normalized rate (PT INR) will be collected but not graded.
- UA parameters: Nitrite, urine protein, and urine glucose via dipstick.
  - Note 1: pH, specific gravity, bilirubin, and occult blood will be collected but not graded.
  - Note 2: If urine dipstick is abnormal for blood, protein, glucose, and nitrites, urine microscopy will be performed (for WBC, RBC, and bacteria), and the results will supersede those of the dipstick UA.
- Vital signs (VS) will be collected at Screening, Day -1, within 30 minutes before and 2 hours ( $\pm$  10 minutes) after each dose on Day 1 through Day 7, and the mornings of Days 8 and 9.
  - Supine VS parameters: Body temperature (oral), systolic blood pressure (SBP), diastolic BP (DBP), pulse, and respiratory rate.
    - Note 1: BP will be taken after at least 5 minutes of resting.
  - Orthostatic VS parameters: SBP, DBP, and pulse
    - Note 1: Orthostatic parameters will be measured 1 minute  $\pm$  15 seconds and 3 minutes  $\pm$  15 seconds after standing.
- Electrocardiogram (ECG) results will be collected at Screening, Day -1, and prior to the morning dose on Day 4, and Day 8 (before 12h PK timepoint after Day 7 evening dose) or at early termination.

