**Table 8: Laboratory Adverse Event Grading Scale (continued)**

Parameter	Grade 1/Mild	Grade 2/Moderate	Grade 3/Severe	Grade 4/ Potentially Life-Threatening
change from baseline				
Platelets decrease – $\times 10^3/\mu\text{L}$	125 – 140	100 – 124	25 – 99	< 25
Leukocytes (WBC) increase – $\times 10^3/\mu\text{L}$	10.80 – 15.00	15.01 – 20.00	20.01 – 25.00	> 25.00
Leukocytes (WBC) decrease – $\times 10^3/\mu\text{L}$	2.50 – 3.50	1.50 – 2.49	1.00 – 1.49	< 1.00
Lymphocytes decrease – $\times 10^3/\mu\text{L}$	0.75 – 1.00	0.50 – 0.74	0.25 – 0.49	< 0.25
Monocytes increase – $\times 10^3/\mu\text{L}$	1.01 – 2.00	2.01 – 3.00	> 3.00	Intervention indicated
Basophils increase – $\times 10^3/\mu\text{L}$	0.16 – 0.50	0.51 – 0.80	> 0.80	Intervention indicated
Eosinophils increase – $\times 10^3/\mu\text{L}$	0.65 – 1.50	1.51 – 5.00	> 5.0	Hyper-eosinophilic
Neutrophils decrease – $\times 10^3/\mu\text{L}$	1.50 – 2.00	1.00 – 1.49	0.50 – 0.99	< 0.50
Coagulation				
Prothrombin Time – sec	11.2 – 12.3	12.4 – 13.4	13.5 – 14.0	> 14.0
Activated Partial Thromboplastin Time (aPTT) – sec	35.0 – 42.0	42.1 – 49.0	49.1 – 52.5	> 52.5
Urine Dipstick				
Nitrite	1+	2+	>2+	--
Urine Protein	Trace	1+	2+	Hospitalization or dialysis
Urine Glucose	Trace	1+	2+	Hospitalization for hyperglycemia
Urine Microscopy				
White blood cells (WBC) per HPF	0 – 10	11 – 50	> 50 or gross	Hospitalization or intervention
Red blood cells (RBC) per HPF	1 – 10	11 – 50	> 50 or gross	Hospitalization or packed red blood cells (PRBC) transfusion
Bacteria (microscopic)	Few	Moderate	Many	Hospitalization or intervention

 Liver function tests (LFT) include ALT and AST. Urine microscopy was only performed if urine dipstick was abnormal for blood, protein, glucose, and nitrites. The results of the urine microscopy would supersede the results of the urine dipstick.

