## 14.2 Tolerability Data

**Table 14: Tolerability by Treatment Group, Safety Population**

Participants who:	400 mg SLV213 (N=X)		Placebo (N=X)	
	n	%	n	%
Terminated early or withdrawn due to TEAE related to study product	x	xx	xx	xx
Have at least one TEAE				
Met Grade 3 abnormal criteria at least once post-dose for				
Safety laboratory tests				
VS measurements				
Safety ECG parameters				
Completed all oral medication doses				

Note: N = Number of participants in the Safety Population; n = Number of participants meeting each tolerability category criteria.

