### 16.2.8 Individual Laboratory Measurements

**[Implementation Note:** These listings (for hematology, chemistry, coagulation, and urinalysis) include all laboratory results, scheduled and unscheduled. These listings are not color-coded, but the severity should be included in parentheses after the result for abnormal results, e.g., 16.2 (Mild).

Measurements outside the reference range but are not graded should show “ONR” for “Severity Grade”. Change from Baseline column will be blank for non-numeric parameters and a dash (-) for baseline time point.

Refer to [Section 9.6](#) for sort order of laboratory parameters.

Listing will be sorted by Treatment Group, Participant ID, Parameter, Time Point, and Assessment Time. Refer to [Section 9.6](#) for parameter sort orders.]

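### Read literally, SAP Table 8 and the ONR rule in SAP 9.6 leave a 3+ or 4+ urine protein or glucose ungraded while a 2+ counts as Grade 3

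*SAP*

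**What the plan says.** SAP 4.5.1 names the graded dipstick tests: "UA parameters: Nitrite, urine protein, and urine glucose via dipstick". Their cut-points are in the urine dipstick block of SAP Table 8. The protein row reads "Urine Protein Trace 1+ 2+ Hospitalization or dialysis" and the glucose row reads "Urine Glucose Trace 1+ 2+ Hospitalization for hyperglycemia". In both, Grade 3 is a single reading and Grade 4 is an event rather than a reading.

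SAP 9.6 deals with abnormal values that match no printed grade: "Laboratory results outside of normal range but not within toxicity grading ranges will be listed as" ONR. The implementation note for the individual laboratory listings (16.2.8) says the same: "Measurements outside the reference range but are not graded should show" ONR.

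The protocol is narrower. In sections 8.3.3 and 8.5.6, the post-dose values left ungraded are those that "are less than Grade 1 in the toxicity table, will not be graded and reported as outside the normal range".

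The count at stake is in SAP Table 14, under "Met Grade 3 abnormal criteria at least once post-dose for" safety laboratory tests. SAP section 3 lists this item among the primary tolerability endpoints.

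**The concern.** A severity scale should not fall as the measurement gets worse. Here 2+ protein is Grade 3, but no cell holds 3+, and the SAP does not leave that case to judgement: its ONR rule catches every abnormal value outside the printed grades, on either side. ONR is not a grade.

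If the rule is programmed as written, a participant with a worse dipstick result is left out of a primary tolerability count that a participant with a milder result enters. Table 36, which follows the Table 33 layout, has rows for None through Life-Threatening and none for ONR, so an ungraded 3+ has no natural place there except None. Inclusion criterion 4 requires urine protein to be within the laboratory normal range, so a high post-dose protein would be a new finding.

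**Working it through.** The plan gives no figure to reproduce. The check is a lookup of each possible reading against the printed rules, followed by an illustration of the effect on the count.

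**Step 1. Apply Table 8 and the ONR rule as printed.**

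| Reading | Urine protein, urine glucose | Nitrite (same block) |
|---|---|---|
| Trace | Grade 1 | ONR (milder than Grade 1) |
| 1+ | Grade 2 | Grade 1 |
| 2+ | Grade 3 | Grade 2 |
| 3+ | ONR, unless the Grade 4 event occurs | Grade 3 (>2+) |
| 4+ | ONR, unless the Grade 4 event occurs | Grade 3 (>2+) |

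The order reverses above 2+ for protein and glucose only.

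**Step 2. Compare with similar rows of Table 8.** Where Grade 4 is an event, a condition or blank, the other rows leave Grade 3 open-ended: BUN (>31), fasting serum glucose (>125), carbon dioxide (>40.0 and <14.0), total protein (<5.0), albumin (<2.5), monocytes (>3.00), basophils (>0.80), eosinophils (>5.0), nitrite (>2+), and urine white and red cells (>50 or gross). Urine bacteria ends in a terminal category, Many. Only urine protein and urine glucose stop at one reading.

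**Step 3. Look for another rule that supplies a grade.** SAP 4.5.1 says that, when triggered, "urine microscopy will be performed (for WBC, RBC, and bacteria), and the results will supersede those of the dipstick UA". None of those three is protein or glucose, so microscopy gives no grade for either.

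**Step 4. Size the effect on one count.** Suppose one SLV213 participant has a 3+ result, no Grade 4 event and no other Grade 3 laboratory result. Table 14 prints only n and %, so the exact (Clopper-Pearson) 95% intervals are added here for scale. For x = 0 the upper limit is 1 − 0.025^(1/n). For x = 1 the lower limit is 1 − 0.975^(1/n), and the upper limit is the p that solves (1 − p)^n + n·p·(1 − p)^(n−1) = 0.025.

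- Planned n = 8 (SAP section 5), as written: 0/8 = 0%, upper limit 1 − 0.025^(1/8) = 36.9%.
- n = 8, with 3+ counted as Grade 3: 1/8 = 12.5%, interval 0.3% to 52.7%.
- n = 12, as written: 0/12 = 0%, upper limit 26.5%.
- n = 12, with 3+ counted as Grade 3: 1/12 = 8.3%, interval 0.2% to 38.5%.

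The n = 12 case assumes that all four replacement participants in SAP 6.2 received SLV213; the SAP does not say so. The Safety Population includes replacements. SAP Table 4 prints 6 for this arm against 8 in section 5, so the denominator is itself unsettled.

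**The case against.** The best defence is that the ONR sentence is only a display convention. It follows the description of the listings, the SAP says it expands on the protocol, and the protocol leaves ungraded only values below Grade 1. A 3+ is not below Grade 1, and an analyst could reasonably read 2+ as 2+ or more. Protocol 8.3.3 also treats abnormal post-treatment laboratory values as adverse events, and SAP 4.5.1 has all adverse events graded by qualified staff. This shows that a reversal was not intended. It does not remove it: the SAP drops the protocol's limit, states its own rule twice, and nowhere says that 2+ means 2+ or more. An investigator's grade would appear in the adverse event tables, whereas the Table 14 row asks whether the laboratory criteria were met.

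A reader might infer that ungraded results could also have escaped the Grade 3 halting rules in protocol 7.1.1 and 7.1.2. The documents do not support this. Those rules act on events graded by the site investigator under the protocol, and the SAP already reports that the study stopped after Cohort 1, so its labelling rule could not have governed a halting decision. Nor is the result lost: it remains in Table 32 and Listing 16.

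Three further points stand. The strip is not named, and the nitrite cell shows only that readings above 2+ are foreseen for nitrite. The protocol takes its grading from an FDA scale by reference, and its own supplement (Appendix A) has no urine protein or glucose row, so whether these cells depart from their source cannot be checked here. And the rule that microscopy supersedes the dipstick, read as literally as the ONR rule, might displace a 2+ grade too, which is a separate ambiguity.

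**Conclusion.** The point holds as a flaw in the SAP's written rules for the final analysis. For two of the three graded dipstick tests, the printed grades and the ONR rule together put a worse reading below a milder one in a primary tolerability count and in Table 36.

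The size is at most one participant per qualifying case: 12.5 percentage points with 8 SLV213 participants, or 8.3 with 12. It rests on the strip reporting above 2+ for these analytes, on no Grade 4 event, on no other Grade 3 laboratory result in that participant, and on microscopy not being taken to replace the protein or glucose grade. If the strip stops at 2+, nothing changes. The correction should be made before lock because it is cheap and the tables are still to be produced. Nothing here suggests that any safety decision already taken was affected.

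**What to change.** Issue a SAP addendum before final data lock; SAP section 15 allows this and rules out amendment afterwards.

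- In Table 8, change the Grade 3 entries for urine protein and urine glucose from 2+ to 2+ or greater. This takes the open-ended form of the comparable rows. It does not take nitrite's cut-point, since a 2+ nitrite is Grade 2.
- In SAP 9.6 and the note at 16.2.8, state that ONR applies only to abnormal values milder than the Grade 1 limit, or to parameters or directions with no grading scale. The second clause is needed so that eGFR, direct bilirubin, red blood cells, PT INR and high platelets keep the label. This restores consistency with protocol 8.3.3 and 8.5.6.

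Widening the Table 14 row to Grade 3 or higher would not be enough, because the affected result has no grade at all.

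The cost is two table cells and one sentence, repeated in the listing note. The Grade 3 laboratory count may rise slightly.
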